Appendix 6: Method for computing height velocity values and z-scores for individual subjects

For each subject, a height velocity value will be assigned to each calendar year according to the following algorithm:

Notations:

AB = age at baseline height measurement (Months)

A1 = age at measurements assigned to years 1 (months)

HB = height at baseline (cm)

H1 = height at measurements assigned to years 1 (cm)

HV1 = height velocity at measurements assigned to years 1 (cm/year); computed only if the corresponding year was assigned a non-missing height.

Note: HB and AB are required to be non-missing for all subjects included in the height velocity analysis

Year	Time Interval (months)	Assigned height value (cm)	Assigned height velocity value (cm/year)
1	[AB, AB+12)	H1 = height value closest to the upper limit of the time interval	If H1 is non-missing, $HV1 = 12 * (H1 - HB) / (A1 - AB)$ If H1 is missing then HV1 is missing

For each non-missing height velocity value assigned to a year, the z-score will be computed as

Year	Z-score
1	If HV1 is non-missing, $Z1 = (HV1 - \text{Mean at mid-point age in years MA1}) / \text{Standard deviation at age MA1}$, where the mid-point age in years $MA1 = ((A1 + AB) / 2) / 12 = (A1 + AB) / 24$ (rounded to closest first decimal) and the mean (same as 50th percentile) and standard deviation (SD) will be read from the following tables with height velocity normative data for the corresponding gender and mid-point age in years MA1 If HV1 is missing then Z1 is missing

Height Velocity Normative Data Based on Tanner et al^[6]**Notes:**

The 3rd, 50th and 97th percentiles are interpolated from the height velocity charts from Tanner et

al^[6] for the average maturing children. These percentiles were provided by [name], who used them in his previous research.

Mean and standard deviation (SD) derived based on the normal (and therefore symmetrical) distribution assumption:

Mean = 50th percentile

SD = [(50th percentile – 3rd percentile) + (97th percentile – 50th percentile)]/2*1.88

The 2.5 years mean and SD is applied for all subjects with age 2 - 2.5 years. For girls, the 15.5 years mean is applied for subjects with age >15.5 years, the 14.5 years SD is applied for subjects age >14.5 years; For boys, the 17.5 years mean and SD is applied for all subjects with age > 17.5 years. The values carried forward have been filled up to age 18.5 years for both boys and girls.

Girls:

AGE (YEARS)	50th percentile / Mean	3rd percentile	97th percentile	Derived SD
2.5	8.6	5.9	11.3	1.4
2.6	8.5	5.8	11.2	1.4
2.7	8.4	5.7	11.0	1.4
2.8	8.3	5.7	10.9	1.4
2.9	8.2	5.6	10.7	1.4
3.0	8.1	5.5	10.6	1.4
3.1	8.0	5.4	10.5	1.3
3.2	7.9	5.4	10.3	1.3
3.3	7.8	5.3	10.2	1.3
3.4	7.7	5.3	10.0	1.3
3.5	7.6	5.2	9.9	1.3
3.6	7.5	5.1	9.8	1.2
3.7	7.4	5.1	9.7	1.2
3.8	7.4	5.0	9.5	1.2
3.9	7.3	5.0	9.4	1.2
4.0	7.2	4.9	9.3	1.2
4.1	7.1	4.9	9.2	1.2
4.2	7.0	4.8	9.2	1.2
4.3	7.0	4.8	9.1	1.2
4.4	6.9	4.7	9.1	1.1
4.5	6.8	4.7	9.0	1.1
4.6	6.8	4.7	8.9	1.1
4.7	6.7	4.7	8.8	1.1
4.8	6.7	4.6	8.8	1.1
4.9	6.6	4.6	8.7	1.1
5.0	6.6	4.6	8.6	1.1
5.1	6.6	4.6	8.5	1.1
5.2	6.5	4.6	8.5	1.0
5.3	6.5	4.5	8.4	1.0
5.4	6.4	4.5	8.4	1.0
5.5	6.4	4.5	8.3	1.0
5.6	6.4	4.5	8.2	1.0
5.7	6.3	4.5	8.2	1.0
5.8	6.3	4.4	8.1	1.0
5.9	6.2	4.4	8.1	1.0
6.0	6.2	4.4	8.0	1.0
6.1	6.2	4.4	8.0	1.0
6.2	6.2	4.4	7.9	0.9
6.3	6.1	4.3	7.9	0.9
6.4	6.1	4.3	7.8	0.9
6.5	6.1	4.3	7.8	0.9

AGE (YEARS)	50th percentile / Mean	3rd percentile	97th percentile	Derived SD
6.6	6.1	4.3	7.8	0.9
6.7	6.1	4.3	7.7	0.9
6.8	6.0	4.3	7.7	0.9
6.9	6.0	4.3	7.6	0.9
7.0	6.0	4.3	7.6	0.9
7.1	6.0	4.3	7.6	0.9
7.2	6.0	4.3	7.6	0.9
7.3	5.9	4.3	7.5	0.9
7.4	5.9	4.3	7.5	0.9
7.5	5.9	4.3	7.5	0.9
7.6	5.9	4.3	7.5	0.9
7.7	5.9	4.3	7.5	0.9
7.8	5.8	4.2	7.4	0.9
7.9	5.8	4.2	7.4	0.9
8.0	5.8	4.2	7.4	0.9
8.1	5.8	4.2	7.4	0.8
8.2	5.8	4.2	7.4	0.8
8.3	5.7	4.2	7.3	0.8
8.4	5.7	4.2	7.3	0.8
8.5	5.7	4.2	7.3	0.8
8.6	5.7	4.2	7.3	0.8
8.7	5.7	4.2	7.3	0.8
8.8	5.7	4.2	7.3	0.8
8.9	5.7	4.2	7.3	0.8
9.0	5.7	4.2	7.3	0.8
9.1	5.7	4.2	7.3	0.8
9.2	5.7	4.2	7.3	0.8
9.3	5.8	4.3	7.4	0.8
9.4	5.8	4.3	7.4	0.8
9.5	5.8	4.3	7.4	0.8
9.6	5.9	4.3	7.5	0.9
9.7	6.0	4.3	7.6	0.9
9.8	6.0	4.4	7.8	0.9
9.9	6.1	4.4	7.9	0.9
10.0	6.2	4.4	8.0	1.0
10.1	6.3	4.5	8.1	1.0
10.2	6.4	4.5	8.3	1.0
10.3	6.5	4.6	8.4	1.0
10.4	6.6	4.6	8.6	1.0
10.5	6.7	4.7	8.7	1.1
10.6	6.9	4.9	8.9	1.1
10.7	7.1	5.1	9.1	1.1
10.8	7.4	5.3	9.3	1.1
10.9	7.6	5.5	9.5	1.1
11.0	7.8	5.7	9.7	1.1

AGE (YEARS)	50th percentile / Mean	3rd percentile	97th percentile	Derived SD
11.1	7.9	5.8	9.8	1.1
11.2	8.0	5.9	10.0	1.1
11.3	8.1	5.9	10.1	1.1
11.4	8.2	6.0	10.3	1.1
11.5	8.3	6.1	10.4	1.1
11.6	8.1	5.9	10.2	1.2
11.7	7.9	5.7	10.1	1.2
11.8	7.7	5.5	9.9	1.2
11.9	7.5	5.3	9.8	1.2
12.0	7.3	5.1	9.6	1.2
12.1	7.0	4.8	9.3	1.2
12.2	6.7	4.5	9.0	1.2
12.3	6.5	4.2	8.6	1.2
12.4	6.2	3.9	8.3	1.2
12.5	5.9	3.6	8.0	1.2
12.6	5.6	3.3	7.7	1.1
12.7	5.3	3.1	7.3	1.1
12.8	4.9	2.8	7.0	1.1
12.9	4.6	2.6	6.6	1.1
13.0	4.3	2.3	6.3	1.1
13.1	4.0	2.1	6.0	1.0
13.2	3.8	1.9	5.7	1.0
13.3	3.5	1.6	5.4	1.0
13.4	3.3	1.4	5.1	1.0
13.5	3.0	1.2	4.8	1.0
13.6	2.8	1.0	4.5	0.9
13.7	2.5	0.9	4.2	0.9
13.8	2.3	0.7	3.8	0.8
13.9	2.0	0.6	3.5	0.8
14.0	1.8	0.4	3.2	0.7
14.1	1.6		2.9	0.7
14.2	1.4		2.6	0.6
14.3	1.3		2.4	0.6
14.4	1.1		2.1	0.5
14.5	0.9		1.8	0.5
14.6	0.8			0.5
14.7	0.7			0.5
14.8	0.6			0.5
14.9	0.5			0.5
15.0	0.4			0.5
15.1	0.3			0.5
15.2	0.3			0.5
15.3	0.2			0.5
15.4	0.2			0.5
15.5	0.1			0.5

AGE (YEARS)	50 th percentile / Mean	3 rd percentile	97 th percentile	Derived SD
15.6	0.1			0.5
15.7	0.1			0.5
15.8	0.1			0.5
15.9	0.1			0.5
16.0	0.1			0.5
16.1	0.1			0.5
16.2	0.1			0.5
16.3	0.1			0.5
16.4	0.1			0.5
16.5	0.1			0.5
16.6	0.1			0.5
16.7	0.1			0.5
16.8	0.1			0.5
16.9	0.1			0.5
17.0	0.1			0.5
17.1	0.1			0.5
17.2	0.1			0.5
17.3	0.1			0.5
17.4	0.1			0.5
17.5	0.1			0.5
17.6	0.1			0.5
17.7	0.1			0.5
17.8	0.1			0.5
17.9	0.1			0.5
18.0	0.1			0.5
18.1	0.1			0.5
18.2	0.1			0.5
18.3	0.1			0.5
18.4	0.1			0.5
18.5	0.1			0.5

Boys:

AGE (YEARS)	50 th percentile / Mean	3 rd percentile	97 th percentile	Derived SD
2.5	8.3	5.7	10.9	1.4
2.6	8.2	5.6	10.8	1.4
2.7	8.1	5.6	10.6	1.3

AGE (YEARS)	50th percentile / Mean	3rd percentile	97th percentile	Derived SD
2.8	8.0	5.5	10.5	1.3
2.9	7.9	5.5	10.3	1.3
3.0	7.8	5.4	10.2	1.3
3.1	7.7	5.3	10.1	1.3
3.2	7.6	5.3	10.0	1.2
3.3	7.6	5.2	9.8	1.2
3.4	7.5	5.2	9.7	1.2
3.5	7.4	5.1	9.6	1.2
3.6	7.3	5.1	9.5	1.2
3.7	7.3	5.0	9.4	1.2
3.8	7.2	5.0	9.4	1.2
3.9	7.2	4.9	9.3	1.2
4.0	7.1	4.9	9.2	1.1
4.1	7.0	4.9	9.1	1.1
4.2	7.0	4.8	9.0	1.1
4.3	6.9	4.8	9.0	1.1
4.4	6.9	4.7	8.9	1.1
4.5	6.8	4.7	8.8	1.1
4.6	6.8	4.7	8.8	1.1
4.7	6.7	4.7	8.7	1.1
4.8	6.7	4.6	8.7	1.1
4.9	6.6	4.6	8.6	1.1
5.0	6.6	4.6	8.6	1.1
5.1	6.6	4.6	8.5	1.1
5.2	6.5	4.6	8.5	1.0
5.3	6.5	4.5	8.4	1.0
5.4	6.4	4.5	8.4	1.0
5.5	6.4	4.5	8.3	1.0
5.6	6.4	4.5	8.3	1.0
5.7	6.3	4.4	8.2	1.0
5.8	6.3	4.4	8.2	1.0
5.9	6.2	4.3	8.1	1.0
6.0	6.2	4.3	8.1	1.0
6.1	6.2	4.3	8.0	1.0
6.2	6.1	4.3	8.0	1.0
6.3	6.1	4.2	7.9	1.0
6.4	6.0	4.2	7.9	1.0
6.5	6.0	4.2	7.8	1.0
6.6	6.0	4.2	7.8	1.0
6.7	6.0	4.2	7.8	0.9
6.8	5.9	4.2	7.7	0.9
6.9	5.9	4.2	7.7	0.9
7.0	5.9	4.2	7.7	0.9
7.1	5.9	4.2	7.7	0.9
7.2	5.9	4.2	7.6	0.9

AGE (YEARS)	50th percentile / Mean	3rd percentile	97th percentile	Derived SD
7.3	5.8	4.1	7.6	0.9
7.4	5.8	4.1	7.5	0.9
7.5	5.8	4.1	7.5	0.9
7.6	5.8	4.1	7.4	0.9
7.7	5.7	4.0	7.4	0.9
7.8	5.7	4.0	7.3	0.9
7.9	5.6	3.9	7.3	0.9
8.0	5.6	3.9	7.2	0.9
8.1	5.6	3.9	7.2	0.9
8.2	5.5	3.9	7.1	0.9
8.3	5.5	3.8	7.1	0.9
8.4	5.4	3.8	7.0	0.9
8.5	5.4	3.8	7.0	0.9
8.6	5.4	3.8	7.0	0.8
8.7	5.4	3.8	6.9	0.8
8.8	5.3	3.8	6.9	0.8
8.9	5.3	3.8	6.8	0.8
9.0	5.3	3.8	6.8	0.8
9.1	5.3	3.8	6.8	0.8
9.2	5.3	3.8	6.8	0.8
9.3	5.2	3.7	6.7	0.8
9.4	5.2	3.7	6.7	0.8
9.5	5.2	3.7	6.7	0.8
9.6	5.2	3.7	6.7	0.8
9.7	5.2	3.7	6.6	0.8
9.8	5.1	3.7	6.6	0.8
9.9	5.1	3.7	6.5	0.8
10.0	5.1	3.7	6.5	0.7
10.1	5.1	3.7	6.5	0.7
10.2	5.1	3.7	6.5	0.7
10.3	5.1	3.7	6.5	0.7
10.4	5.1	3.7	6.5	0.7
10.5	5.1	3.7	6.5	0.7
10.6	5.1	3.7	6.5	0.8
10.7	5.1	3.7	6.5	0.8
10.8	5.2	3.7	6.6	0.8
10.9	5.2	3.7	6.6	0.8
11.0	5.2	3.7	6.6	0.8
11.1	5.2	3.7	6.6	0.8
11.2	5.2	3.7	6.6	0.8
11.3	5.3	3.8	6.7	0.8
11.4	5.3	3.8	6.7	0.8
11.5	5.3	3.8	6.7	0.8
11.6	5.4	3.8	6.8	0.8
11.7	5.5	3.9	6.9	0.8

AGE (YEARS)	50th percentile / Mean	3rd percentile	97th percentile	Derived SD
11.8	5.5	3.9	7.1	0.8
11.9	5.6	4.0	7.2	0.9
12.0	5.7	4.0	7.3	0.9
12.1	5.9	4.2	7.6	0.9
12.2	6.1	4.3	8.0	1.0
12.3	6.4	4.5	8.3	1.0
12.4	6.6	4.6	8.7	1.1
12.5	6.8	4.8	9.0	1.1
12.6	7.2	5.1	9.4	1.2
12.7	7.6	5.3	9.9	1.2
12.8	7.9	5.6	10.3	1.3
12.9	8.3	5.8	10.8	1.3
13.0	8.7	6.1	11.2	1.4
13.1	8.9	6.3	11.3	1.3
13.2	9.0	6.5	11.5	1.3
13.3	9.2	6.7	11.6	1.3
13.4	9.3	6.9	11.8	1.3
13.5	9.5	7.1	11.9	1.3
13.6	9.3	6.9	11.7	1.3
13.7	9.0	6.7	11.5	1.3
13.8	8.8	6.4	11.2	1.3
13.9	8.5	6.2	11.0	1.3
14.0	8.3	6.0	10.8	1.3
14.1	7.9	5.6	10.4	1.3
14.2	7.6	5.2	10.0	1.3
14.3	7.2	4.9	9.6	1.3
14.4	6.9	4.5	9.2	1.3
14.5	6.5	4.1	8.8	1.3
14.6	6.1	3.7	8.4	1.3
14.7	5.8	3.4	8.1	1.3
14.8	5.4	3.0	7.7	1.3
14.9	5.1	2.7	7.4	1.3
15.0	4.7	2.3	7.0	1.3
15.1	4.4	2.1	6.7	1.2
15.2	4.1	1.9	6.4	1.2
15.3	3.9	1.6	6.1	1.2
15.4	3.6	1.4	5.8	1.2
15.5	3.3	1.2	5.5	1.1
15.6	3.1	1.0	5.2	1.1
15.7	2.9	0.9	4.9	1.1
15.8	2.6	0.7	4.7	1.0
15.9	2.4	0.6	4.4	1.0
16.0	2.2	0.4	4.1	1.0
16.1	2.1		3.9	1.0
16.2	1.9		3.7	0.9

AGE (YEARS)	50th percentile / Mean	3rd percentile	97th percentile	Derived SD
16.3	1.8		3.4	0.9
16.4	1.6		3.2	0.8
16.5	1.5		3.0	0.8
16.6	1.4		2.8	0.8
16.7	1.3		2.7	0.8
16.8	1.1		2.5	0.7
16.9	1.0		2.4	0.7
17.0	0.9		2.2	0.7
17.1	0.8		2.1	0.7
17.2	0.7		2.0	0.6
17.3	0.7		1.8	0.6
17.4	0.6		1.7	0.6
17.5	0.5		1.6	0.6
17.6	0.5			0.6
17.7	0.5			0.6
17.8	0.5			0.6
17.9	0.5			0.6
18.0	0.5			0.6
18.1	0.5			0.6
18.2	0.5			0.6
18.3	0.5			0.6
18.4	0.5			0.6
18.5	0.5			0.6

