Physical activity evaluation ^f	X								
Prestudy AED and other therapy ^g	X								
Randomization		X							
Study Drug									
Dispense study drug		X	X	X	X	X	X		
Study drug accountability			X	X	X	X	X	X	
Pharmacokinetics									
Blood sample collection for quantitation of study drug ^h			X		X	X		X	
Safety									
Physical examination	X	X	X		X	X	X	X	
Neurologic examination	X	X	X		X	X	X	X	
12-lead ECG	X								
Height/weight ⁱ	X	X	X		X	X	X	X	
Vital signs (temperature, HR, RR, BP) ^j	X	X	X		X	X	X	X	
Clinical laboratory tests ^k	X		X		X	X	X	X	
Pregnancy test ^l	X	X	X	X	X	X	X	X	
24-hour urine collection ^m	X					X		X	
Tanner staging ⁿ		X				X		X	

Phase	Screening	Open-Label Treatment ^a						Posttreatment ^b	
		Baseline/ W1	M1	M2	M3	M6	M9	End-of- Study/Early Withdrawal	Follow-up Telephone Contact
Week (W)/Month (M)									
Study Day	≤-28	1 ^c	30	60	90	180	270	360	390 ^d
Study Day Window	-7days	±7days	±7days	±7days	±7days	±7days	±7days	±7days	±7days
Visit ^e	1	2	3	4	5	6	7	8	NA
Renal ultrasound ^o	X					X		X	
Biochemical bone markers ^p	X					X		X	
DEXA scan ^{b,q}		X				X		X	
Bone age x-ray ^f		X						X	
Dispense seizure diary and take-home record ^s		X	X	X	X	X	X		
Review seizure diary and take-home record			X	X	X	X	X	X	
Cogstate Battery ^t	X	X				X		X	
Animal Fluency Test NEPSY-II ^u	X	X				X		X	
Vineland Adaptive Behavior Scale ^v		X			X	X		X	
CBCL-Parent Version ^w		X			X	X		X	
C-SSRS ^x		X	X	X	X	X	X	X	
Ongoing Review									
Concomitant therapy	X	X	X	X	X	X	X	X	X
Adverse event monitoring	X	X	X	X	X	X	X	X	X

Footnotes appear on the following page.

^a Includes a titration period of approximately 6 to 8 weeks, followed by a maintenance period.

^b There may be an optional post-study follow-up phase to obtain DEXA measurements in a subgroup of subjects who experience a clinically important reduction (change in Z-score of -0.5 or greater) in BMD, based on local DEXA scan results, after 1 year of treatment with topiramate; these subjects will have a repeat DEXA scan 6 months after discontinuation of study drug.

^c The Day 1 visit will serve as the baseline visit. All procedures on Day 1 (except dispensing of study drug) should be completed before randomization.

^d The site will contact the subject via telephone at Month 13, to collect data on adverse events and concomitant medications.

^e Window for all visits will be ±7 days.

^f Adequacy of physical activity will be assessed with the Habitual Activity Estimation Scale.

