Orthostatic vital signs will be obtained for all subjects pending cooperation of subjects. A set of 3 measurements will be obtained at baseline only, separated by intervals of 10 minutes. Thereafter, only 1 orthostatic vital sign measurement will be taken at all subsequent visits. The method for obtaining orthostatic vital signs will be as follows: subject will be supine for 5 minutes prior to measurement, and standing for 2 minutes prior to measurement.

Physical Examination

Physical examinations and anthropometric measurements, including weight, height, and pubertal stage according to Tanner’s classification,³⁷ will be performed at the times specified in the Time and Events Schedule.

- Height will be assessed using a wall-mounted stadiometer. Height will be read to the nearest 0.1 cm; measures are to be repeated at least 3 times. Based on previous measurements and

clinical judgment, the healthcare professional should discard any extreme results and make additional measurements until 3 approximately consistent measurements are obtained. All 3 final measurements will be recorded in the CRF; all measurements will be recorded into the source documents. To obtain accurate measures, shoes and hair adornments should be removed and the child should be positioned with heels, buttocks, and back of head against the stadiometer.

The healthcare professionals who measure height at each visit must be trained in the standardized procedure. If possible, the same individual and the same equipment should collect all height measurements at each study site, to help ensure consistency of measurements.

All study site personnel performing the height assessment must be blinded to study treatment assignment and the rest of the subjects' data to avoid/minimize bias. A blinded study nurse or other staff will measure the height of the subject and record it in the source documents, or provide it to the unblinded study coordinator for entry into the source documents. The unblinded study coordinator will then enter this data, along with other visit data, into the CRF. The location for the height measurement data should be kept separate from the rest of the study data, and procedures must be in place to ensure maintenance of the blind.

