10.2. Withdrawal From the Study

A subject will be withdrawn from the study for any of the following reasons:

- Lost to follow-up
- Withdrawal of consent
- The investigator or sponsor believes (eg, that for safety or tolerability reasons such as an adverse event) it is in the best interest of the subject to discontinue treatment.
- Death
- Other reasons
- If a female subject becomes pregnant during the study, she must be discontinued from the study and the pregnancy followed to term, if applicable.

During the study, subjects will also be withdrawn if:

- Subject develops status epilepticus not controlled by a single rescue agent.
- At the discretion of the investigator, subject develops any new seizure types or any clinically relevant safety issue.
- Subject requires greater than a 10-day course of medications that may impact bone metabolism, including intravenous or oral steroids, furosemide, growth hormone, NSAIDs, antacids, or calcium/vitamin D supplements.
- Subject develops nephrocalcinosis (diagnosed in any way) or develops a significant clinical adverse event (eg, serious event, treatment-limiting event, or other consideration) diagnosed as being related to a new kidney stone. Ultrasound results that suggest an asymptomatic kidney stone will not necessarily serve as a reason for withdrawal from the study.
- The investigator believes the subject to be at significant risk of suicidal or violent behavior.

If a subject discontinues treatment before the end of the open-label treatment phase, the end-of-study assessments should be obtained.

If a subject is lost to follow-up, every reasonable effort must be made by the study site personnel to contact the subject and determine the reason for discontinuation/withdrawal. The measures taken to follow-up must be documented.

When a subject withdraws before completing the study, the reason for withdrawal is to be documented in the CRF and in the source document. Study drug assigned to the withdrawn subject may not be assigned to another subject. Subjects who withdraw will not be replaced.

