2.6. Time and Events Schedule

The flow chart showing trial phases and timing of treatment and assessments is given in [Table 1](#).

Table 1: Time and Events Schedule

Phase	Screening	Open-Label Treatment ^a						End-of-Study/Early Withdrawal	Follow-up Telephone Contact
		Baseline/ W1	M1	M2	M3	M6	M9		
Week(W)/Month(M)									
Study Day	≤-28	1 ^c	30	60	90	180	270	360	390 ^d
Study Day Window	-7days	±7days	±7days	±7days	±7days	±7days	±7days	±7days	±7days
Visit ^e	1	2	3	4	5	6	7	8	NA
Screening/Administrative									
Informed consent and assent	X								
Inclusion/exclusion criteria	X	X							
Medical/seizure history	X	X							
Physical activity evaluation ^f	X								
Prestudy AED and other therapy ^g	X								
Randomization		X							
Study Drug									
Dispense study drug		X	X	X	X	X	X		
Study drug accountability			X	X	X	X	X	X	
Pharmacokinetics									
Blood sample collection for quantitation of study drug ^h			X		X	X		X	
Safety									
Physical examination	X	X	X		X	X	X	X	
Neurologic examination	X	X	X		X	X	X	X	
12-lead ECG	X								
Height/weight ⁱ	X	X	X		X	X	X	X	
Vital signs (temperature, HR, RR, BP) ^j	X	X	X		X	X	X	X	
Clinical laboratory tests ^k	X		X		X	X	X	X	
Pregnancy test ^l	X	X	X	X	X	X	X	X	
24-hour urine collection ^m	X					X		X	
Tanner staging ⁿ		X				X		X	

CONFIDENTIAL – FOIA Exemptions Apply in U.S.

Table 1: Time and Events Schedule

Phase	Screening	Open-Label Treatment ^a						End-of-Study/Early Withdrawal	Follow-up Telephone Contact
		Baseline/ W1	M1	M2	M3	M6	M9		
Week(W)/Month(M)									
Study Day	≤-28	1 ^c	30	60	90	180	270	360	390 ^d
Study Day Window	-7days	±7days	±7days	±7days	±7days	±7days	±7days	±7days	±7days
Visit ^e	1	2	3	4	5	6	7	8	NA
Renal ultrasound	X					X		X	
Biochemical bone markers	X					X		X	
DEXA scan ^{b,q}		X				X		X	
Bone age x-ray		X						X	
Dispense seizure diary and take-		X	X	X	X	X	X		
Review seizure diary and take-			X	X	X	X	X	X	
Cogstate Battery ^r	X	X				X		X	
Animal Fluency Test NEPSY-II ^u	X	X				X		X	
Vineland Adaptive Behavior Scale ^v		X			X	X		X	
CBCL-Parent Version ^w		X			X	X		X	
C-SSRS ^x		X	X	X	X	X	X	X	
Ongoing Review									
Concomitant therapy	X	X	X	X	X	X	X	X	X
Adverse event monitoring	X	X	X	X	X	X	X	X	X

Footnotes appear on the following page.

^a Includes a titration period of approximately 6 to 8 weeks, followed by a maintenance period.

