3.1. Visit Windows

The statistical analysis for safety will be based on time intervals that are constructed according to the number of days in trial from day 1. (See table 2-8)

The analysis windows for height, weight, exposure, vital signs, laboratory tests, physical examination and neurological examinations is given in [Table 2](#).

Table 2: Definition of windows for height, weight, exposure, vital signs, laboratory tests, physical examination and neurological examinations:

Scheduled Visit Number	Time Interval (label on output)	Time Interval (Day) ^a	Target Time Point
1,2	Baseline	-35 to 1	1
3	Month 1	2 to 60	30
5	Month 3	61 to 135	90
6	Month 6	136 to 225	180
7	Month 9	226 to 315	270
8	Month 12	≥ 316	360

^a The randomization day is Day 1.

The analysis windows for Renal Ultrasound, Cogstate, Tanner Staging and 24 hour urine collection is given in [Table 3](#).

Table 3: Definition of windows for Renal Ultrasound, Cogstate, Tanner Staging and 24 hour urine collection:

Scheduled Visit Number	Time Interval (label on output)	Time Interval (Day) ^a	Target Time Point
1, 2	Baseline	-35 to 1	1
6	Month 6	2 to 270	180
8	Month 12	≥ 271	360

^a The randomization day is Day 1.

The analysis windows for C-SSRS is given in [Table 4](#).

Table 4: Definition of windows for C-SSRS:

Scheduled Visit Number	Time Interval (label on output)	Time Interval (Day) ^a	Target Time Point
1, 2	Baseline	-35 to 1	1
3	Month 1	2 to 45	30
4	Month 2	46 to 75	60
5	Month 3	76 to 135	90
6	Month 6	136 to 225	180
7	Month 9	226 to 315	270
8	Month 12	>=316	360

^a The randomization day is Day 1.

The analysis windows for Vineland Scale and CBCL is given in [Table 5](#).

Table 5: Definition of windows for Vineland Scale and CBCL:

Scheduled Visit Number	Time Interval (label on output)	Time Interval (Day) ^a	Target Time Point
1, 2	Baseline	-35 to 1	1
5	Month 3	2 to 135	90
6	Month 6	136 to 270	180
8	Month 12	>=271	360

^a The randomization day is Day 1.

The analysis windows for Bone Age is given in [Table 6](#).

Table 6: Definition of windows for Bone age:

Scheduled Visit Number	Time Interval (label on output)	Time Interval (Day) ^a	Target Time Point
1	Baseline	-35 to 180	1
8	Month 12	>=181	360

^a The randomization day is Day 1.

The analysis windows for seizure count is given in [Table 7](#).

Table 7: Definition of windows for seizure count:

Scheduled Visit Number	Time Interval (label on output)	Time Interval (Day) ^a	Target Time Point
3	Month 1	2 to 45	30
4	Month 2	46 to 75	60

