5	Month 3	76 to 135	90
6	Month 6	136 to 225	180
7	Month 9	226 to 315	270
8	Month 12	>=316	360

^a The randomization day is Day 1.

The analysis windows for DEXA is given in [Table 8](#).

Table 8: Definition of windows for DEXA:

Scheduled Visit Number	Time Interval (label on output)	Time Interval (Day) ^a	Target Time Point
1, 2	Baseline	-35 to 30	1
6	Month 6	31 to 270	180
8	Month 12	>=271	360

^a The randomization day is Day 1.

The analysis windows for Pharmacokinetics is given in [Table 9](#).

Table 9: Definition of windows for Pharmacokinetics

Scheduled Visit Number	Time Interval (label on output)	Time Interval (Day) ^a	Target Time Point
3	Month 1	2 to 45	30
5	Month 3	46 to 135	90
6	Month 6	136 to 270	180
8	Month 12	>=271	360

^a: The randomization day is Day 1

Baseline is defined as the last non-missing observation (including an unscheduled visit) prior to or equal to Day 1 (except for DEXA and Bone age, where baseline includes up to 30 days and 180 days post-baseline, respectively).

For post baseline observations, if more than one visit (including an unscheduled visit) occurs in the same time window, the visit nearest to the target day will be used in the analysis. In the case of an equal distance in time, the latest visit will be used.

Data that are not used in the analysis due to multiple observations or being excluded from the above defined time intervals will be displayed in the data listing.

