7.3. Height

Observed height values, change from baseline, Z-scores for height, change from baseline in Z-scores for height, height velocity at 1 year, and height velocity Z-score will be summarized by visit using descriptive statistics. Height, Z-scores for height, height velocity and height velocity Z-scores will be calculated as the mean of the three measurements. The number and percentage of subjects with a height Z-score decrease of >0.5 , >1.0 , and >2.0 will be listed and summarized by visit using descriptive statistics. MMRM analysis will also be performed for changes from baseline and changes in Z-Scores from baseline.

The change in height z-scores will also be summarized by subject's serum bicarbonate categories.

Height velocity values and associated Z-scores will be computed for each post-baseline year in the study, based on the methods described in [Appendix 6](#).

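### Year 1 height velocity drops a height taken at or after 12.0 months and annualises short intervals with no minimum length (minor)

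*SAP*

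**What the plan says.** SAP Appendix 6 assigns one height to Year 1 from an interval that includes the baseline age AB and stops short of AB+12 months. The height chosen is "H1 = height value closest to the upper limit of the time interval". Velocity is HV1 = 12 × (H1 − HB)/(A1 − AB), computed whenever H1 is not missing. Its Z-score uses a normative mean and SD for annual velocity. Neither Appendix 6 nor SAP 7.3 sets a smallest A1 − AB, and no later year is defined.

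The visit windows are different. In SAP 3.1, Table 2 ("Definition of windows for height, weight, exposure, vital signs, laboratory tests, physical examination and neurological examinations") labels any height from Day 316 as Month 12, with target Day 360 and no upper limit. The schedule allows ±7 days, so an on-schedule Month 12 visit runs from Day 353 to Day 367.

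On the starting point, SAP 3.1 states: "Baseline is defined as the last non-missing observation (including an unscheduled visit) prior to or equal to Day 1". Footnote c of the Protocol's Time and Events Schedule states: "The Day 1 visit will serve as the baseline visit". On early leavers, Protocol 10.2 states: "If a subject discontinues treatment before the end of the open-label treatment phase, the end-of-study assessments should be obtained".

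On measurement, Protocol 9.3 has staff discard extreme readings and "make additional measurements until 3 approximately consistent measurements are obtained". SAP 7.3 adds: "Height, Z-scores for height, height velocity and height velocity Z-scores will be calculated as the mean of the three measurements".

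**The concern.** Two features of the rule sit badly with a result reported as velocity at one year.

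First, the open upper end. A child seen on the last allowed day of the Month 12 window has a height that Table 2 uses as Month 12 for height and height Z-score but that Appendix 6 ignores for velocity. A height further from one year is annualised in its place.

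Second, the missing lower limit. A child whose last height falls near Day 30 still receives a one-year velocity. That value describes only part of the early dosing period, since footnote a of the schedule in SAP 2.6 says the treatment phase "Includes a titration period of approximately 6 to 8 weeks, followed by a maintenance period". The height change is inflated about twelvefold, measurement error included, and is then judged against the SD of growth over a full year.

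Velocity and its Z-score appear in the list of key safety endpoints in Protocol 11.4. What is at stake is the readability of that summary and of individual outlying values.

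**Working it through.** **Normative SDs.** The tabled SDs reproduce as (97th − 3rd percentile)/(2 × 1.88): girls 8.5 years (7.3 − 4.2)/3.76 = 0.82 (table 0.8); boys 10.0 years (6.5 − 3.7)/3.76 = 0.74 (table 0.7); girls 2.5 years (11.3 − 5.9)/3.76 = 1.44 (table 1.4).

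**Interval and multiplier.** With a Day 1 baseline, months = (day − 1)/30.4375 and multiplier = 12/months.

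| Day | Months | Multiplier | Status |
|---|---|---|---|
| 30 | 0.953 | 12.6 | eligible |
| 90 | 2.924 | 4.10 | eligible |
| 180 | 5.881 | 2.04 | eligible |
| 270 | 8.838 | 1.36 | eligible |
| 316 | 10.349 | 1.16 | eligible |
| 360 | 11.795 | 1.02 | eligible |
| 366 | 11.992 | 1.00 | eligible |
| 367 | 12.02 | (1.00) | dropped |

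**Upper end.** With exact ages, one day of the 15-day visit window is lost, plus any later visit. The replacement is Month 9 unless that height is missing or a later unscheduled height falls inside the interval.

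Appendix 6 does not give the precision of AB and A1. SAP 5.1 uses one-decimal months for height and weight Z-scores, which may or may not apply here. Rounding the interval that way turns Day 365 (11.959) and Day 366 (11.992) into 12.0, so Days 365 to 367 are all lost, and Day 30 becomes 1.0 month with a multiplier of 12.0. Rounding AB and A1 separately can move the interval by up to 0.1 month (about 3 days), so the cut would then vary by child.

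**Error in one child's velocity.** The documents give no height error, so assume a single-reading error e of 0.1, 0.2 or 0.3 cm with three readings averaged. Velocity error SD = multiplier × √2 × e/√3:

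- Day 30: 1.0, 2.1, 3.1 cm/year
- Day 270: 0.11, 0.22, 0.33 cm/year
- Day 360: 0.08, 0.17, 0.25 cm/year

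Against a normative SD of 0.9, typical of many ages in the table, the Day 30 figures are 1.1, 2.3 and 3.4 Z units.

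**Spread in a group.** The documents give no dropout timing either. Assume the planned 29% leave evenly from month f to month 12, completers are measured at 11.8 months and true Z has SD 1:

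Var(Z) = 1 + (12√2·e/(0.9√3))² × [0.71/11.8² + 0.29/(12 − f) × (1/f − 1/12)]

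Example, e = 0.2 and f = 1: 1 + 4.741 × (0.00510 + 0.02417) = 1.139, so SD = 1.07.

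| Leaving starts | e = 0.1 | e = 0.2 | e = 0.3 |
|---|---|---|---|
| 1 week (f = 0.25) | 1.06 | 1.22 | 1.44 |
| 1 month | 1.02 | 1.07 | 1.15 |
| 3 months | 1.01 | 1.03 | 1.07 |
| Everyone at 11.8 months (bracket = 1/11.8²) | 1.00 | 1.02 | 1.04 |

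Simulating the one-month case gives |Z| > 3 in 0.3%, 0.7% and 1.3% of children. In a planned arm of 141, the middle value is 0.007 × 141 = 1.0 child.

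**The case against.** The strongest reply is that this is a descriptive safety table. SAP 7 plans no formal testing, the MMRM in SAP 7.3 is run on height and height Z-score changes, and SAP section 1 names BMD, height and weight Z-scores, not velocity, as the key endpoints of its interim analyses. The summaries show median, minimum and maximum, so an extreme value is visible. All of this stands, and it is why the point is minor.

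A half-open interval is a natural way to assign heights to successive years. That would be a good answer if a second year existed. Appendix 6 defines only Year 1, so a height at 12.0 months or later contributes to no velocity at all. SAP 3.1 lists unused data, but listing does not restore the value.

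The Day 30 case is narrow. Protocol 10.2 asks for final assessments at withdrawal, so a child leaving at Month 2 should have a height then. The large multiplier needs withdrawal near Day 30, or loss before any later height. The 29% also overstates short intervals if read as leavers: Protocol 10.1 counts as non-completers children who add another AED and stay to Month 12, and they have Month 12 heights. Both points stand. Enrolment stopped early as well, so fewer children are affected than planned numbers suggest.

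A reader might infer that velocity should be set to missing below some minimum interval. The documents give no basis for a cut-off. Under the even-dropout assumption, 0.29 × (c − f)/(12 − f) of children would lose a value: 14% to 18% with c at Day 226 (7.392 months) and 5% to 10% at Day 136 (4.435 months). All are early leavers in a safety study, removed to reduce noise that does not move the mean. That is a trade-off, not a correction.

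**Conclusion.** The point holds as a minor defect in a stated rule. The open upper end makes the SAP treat one measurement as Month 12 in Table 2 and as unusable in Appendix 6. The lack of a minimum interval lets very short follow-up be reported as one-year velocity, which widens the distribution modestly and produces a few individual Z-scores that may be mostly measurement error.

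Three stronger readings are not supported:

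- **Month 12 heights are generally lost.** An on-time Day 360 height is at 11.8 months and is kept. A screening baseline would widen the loss (from Day −7, Day 360 is 366 days or 12.02 months later), but it applies only if the scheduled Day 1 height is missing.
- **The treatment comparison is biased by measurement error.** Such error has no direction here, and the documents do not say how early leaving differs by arm.
- **The main growth results are affected.** Height and height Z-score use Table 2, not Appendix 6.

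The multipliers follow from the SAP's own formula with a Day 1 baseline. The spread figures rest on assumed height error and dropout timing. The number of children actually affected cannot be found from the documents.

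**What to change.** In Appendix 6:

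1. Define H1 as the post-baseline height closest to AB+12 months, with no open upper limit. No child is lost. Requiring a post-baseline height also closes a gap: the interval now includes AB itself, so a child with no later height could be given the baseline as H1 and a velocity of 0/0.
2. State the precision of AB and A1.
3. Keep the all-subjects velocity summary. Add a second summary restricted to children whose H1 falls in the Table 2 Month 12 window (Day 316 or later, multiplier at most about 1.16 from a Day 1 baseline).
4. List A1 − AB for each child beside the velocity and its Z-score.

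Table 2 picks the visit nearest Day 360, while this rule picks the height nearest 12 months (about Day 366). With heights on Days 358 and 367 the two would differ, though both lie in the Month 12 window; one sentence acknowledging this is enough.

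The cost is a wording change, a small program change, one extra table and one listing column. The restricted table describes mainly children who stayed to Month 12, which is why it should stand beside the all-subjects summary and not replace it.
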